P-values ≥ 0.0001 will be reported to 4 decimal places; p-values less than 0.0001 will be reported as " <0.0001 ". The mean, standard deviation, and any other statistics other than quantiles, will be reported to one decimal place greater than the original data. Quantiles, such as median, minimum, or maximum will use the same number of decimal places as the original data. Estimated parameters, not on the same scale as raw observations (e.g. regression coefficients) will be reported to 3 significant figures.

Adherence to interventions

Analysis of both intention-to-treat (ITT) and as-treated populations will be performed. All participants who are randomized to a trial arm will be included in the ITT analyses. Participants who adhere to major engagement criteria for their primary intervention will be included in the as-treated analyses.

Analysis methodology

Aim 1

To compare the impact of two interventions delivered online: 1) a dialogue-based webinar (webinar) using the existing COVID-19 Option Grid conversation aid and, 2) an interactive and, dynamic, and multi-component social media web application (social media website), compared to enhanced usual practice (link to Centers for Disease Control (CDC) vaccine website), on COVID-19 vaccine confidence (primary outcome), and other secondary outcomes among LTCWs. We hypothesize that each intervention will be superior to enhanced usual practice at increasing vaccine confidence (*Hypothesis 1.1*) and that the dialogue-based webinar intervention will be superior to the social media arm at increasing vaccine confidence (*Hypothesis 1.2*).

Corresponding analyses

Primary outcome

The primary outcome is the binary classifier of vaccine confidence derived from the three-item Vaccine Confidence Index (VCI), evaluated at 3 weeks post-randomization, which will be analyzed by randomization arm. The determined binary predictors of intervention outcomes will be compared using two-proportion z-tests to identify significant differences between each intervention and enhanced usual practice (Arm 1 vs Arm 3 & Arm 2 vs Arm 3 - superiority analyses) and between the intervention arms (Arm 1 vs Arm 2 - two-tailed equivalency analysis).

Secondary outcomes

- *Change from baseline in COVID-19 Vaccine Confidence.* Analysis of change from

baseline will be based on a binary classifier whether the average score increases (1) or does not increase (2) at T1, T2, and T3 versus baseline.

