Change from baseline in COVID-19 Vaccine Confidence. Looking deeper at the change in vaccine confidence, analyses will consider (a) the proportion of positive (agree and strongly agree) responses in the VCI, (b) positive responses in each of the three VCI questions. Significant correlates with demographic, contextual, and study variables will be evaluated.

External contextual factors. Outside of the study surveys and throughout the trial, we will monitor external factors that may impact participants' views and actions towards the COVID-19 vaccines. This may include monitoring policy and mandate changes for LTCWs and changes in the nature of the pandemic, among other things.

Additional analyses. Any unvalidated thresholds utilized in the primary or secondary analyses will be evaluated for sensitivity to the choice of threshold in ROC analyses. Nonlinear higher-dimensional effects and interactions among variables will be identified by identifying positive or negative outcomes grouped around specific baseline characteristics that are highly unlikely to result from random chance.

Duplicate and missing data

Participants must complete a baseline (T0) survey to be considered enrolled in the study. In the event of duplicate complete T0 submissions, the first complete survey will be used. For participants who complete duplicate follow-up surveys (T1, T2 or T3), the first complete survey

will also be used. In order to be included in primary and secondary outcome analyses, participants must have valid primary outcome data at both T0 and T1.

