The study team will endeavor to minimize missing data; however, it is possible that efforts to ensure complete data collection within the response windows will be unsuccessful or because participants may choose not to respond to one or more questions. Should any primary and/or secondary outcome variables have >5% missing data, the reasons for any missing data will be considered through an analysis for common baseline characteristics of individuals with specific responses missing, those who were lost to follow-up, and those who did not respond to one or more evaluations but were not lost to follow-up. Specific questions with significantly higher rates of missing data will be reviewed for wording bias or missing response options. Based on these considerations, a stochastic outcome set model will be created using multiple imputation and Bayesian methods, as appropriate, to provide a high confidence range for imputed values. Using this approach, an expected result and confidence intervals will be produced for the missing data and the resulting analysis of the full data set, taking into account the statistical uncertainty attributed to the missing data. If available, data from both baseline and subsequent follow-up evaluations will be used in imputing missing results (e.g., responses from T0 and T2 evaluations could be used to impute T1 responses) through multiple imputation regression modeling [3].

Response rates and the frequency of missing data in the ITT and as-treated populations will be reported with the results.

Fraudulent enrollment

Identity verification of some participants will occur after they have completed their journey in the study (using TransUnion's TLOxp verification service). We will also conduct a rigorous review of survey metadata (e.g., IP addresses) and other responses to identify duplicate survey completions or other suspicious survey activity [4,5]. Upon discovery of compelling evidence of fraudulent or illegitimate enrollment, such subjects will be excluded from the study prior to any outcome analyses.

Methods to minimize bias

A naïve analysis will be conducted at the end of the study based only on the unmodified data reflecting ITT assignments of eligible subjects to establish an initial estimator. All primary and secondary analyses will be conducted based on the statistical analysis plan. The statistician member of the DSMB will also independently replicate primary study analyses to confirm their validity.

Multiple testing

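### Appendix B limits the primary analysis to people with T0 and T1 data, yet also includes all randomized and imputes T1, without saying which analysis is primary

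*Combined protocol and SAP*

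**What the plan says.** Three statements in Appendix B bear on who is in the primary analysis.

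- *Adherence to interventions*: "All participants who are randomized to a trial arm will be included in the ITT analyses". Section 4.8.2 likewise puts the Aim 1 and 2 analyses on an ITT basis, alongside an as-treated one.
- *Duplicate and missing data*, first paragraph: "In order to be included in primary and secondary outcome analyses, participants must have valid primary outcome data at both T0 and T1".
- *Duplicate and missing data*, second paragraph: "Should any primary and/or secondary outcome variables have >5% missing data", the reasons for missingness are examined, including among "those who were lost to follow-up, and those who did not respond to one or more evaluations". Multiple imputation and Bayesian methods then follow where appropriate, so that "an expected result and confidence intervals will be produced for the missing data and the resulting analysis of the full data set". The example given is that "responses from T0 and T2 evaluations could be used to impute T1 responses". The section closes: "Response rates and the frequency of missing data in the ITT and as-treated populations will be reported with the results".

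T1, at 3 weeks, is the primary time point. *Methods to minimize bias* adds a naive analysis of unmodified data by ITT assignment, described as a first estimate, and says that the DSMB statistician will replicate the primary analyses. *Multiple testing* sets a threshold of 0.016 for each of the three primary comparisons.

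**The concern.** The completer rule and the imputation plan give different answers for a randomized person without a T1 response: one leaves that person out of the primary analysis, the other imputes the value. Two orderings are possible. Completers could be the naive first look with imputation as the main analysis, or completers could be the main analysis with imputation as support. They name opposite primary analyses, and the text does not choose.

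Arm is shown to the participant at the end of the T0 survey (section 4.7.3), and participants are not blinded (section 4.7.4). Requiring T1 therefore selects the primary contrast on behaviour after allocation. Section 4.4.7 counts not completing surveys as passive withdrawal, so the rule would take such withdrawals out of an analysis labelled ITT. If the choice between the two analyses is left until the data are seen, it cannot be shown to be independent of the results.

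**Working it through.** **1. The plan's own figures.** Section 4.6 claims 80% power for 8 points with 600 per arm, and for 10 points after 40% attrition (600 × 0.60 = 360 per arm), two-sided 0.05. No control rate is given. With an assumed control rate of 0.33, a two-proportion calculation gives 81.9% and 79.1%; with 0.35, 81.2% and 78.3%. The claims are reproducible and nothing here changes them. They assume that losses are random with respect to outcome; no section adopts that as the assumption of the analysis.

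**2. What the rules do to T1.** Over all randomized, imputation of the primary outcome starts once more than 0.05 × 1,800 = 90 people lack T1 confidence data. Inside the T0-and-T1 set that number is always 0, so the planned T1 imputation can never be triggered there. Other secondary items, and T2 or T3 values, could still be missing and imputed. Section 4.6 gives no time point for its 40% attrition. If all of it fell by T1, an extreme case, the two sets would differ by 600 × 0.40 = 240 per arm.

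**3. Completers against the truth.** For Arm 1 versus Arm 3, let m be the share missing T1 and g the responder rate minus the non-responder rate. Each arm's completer rate exceeds its true rate by m × g, so

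bias = m1·g1 − m3·g3.

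All inputs below are assumed:

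| Missing, Arm 1 vs Arm 3 | Gap, both arms | Bias |
|---|---|---|
| 40% vs 40% | 20 points | 0.08 − 0.08 = 0 |
| 20% vs 10% | 10 points | 0.02 − 0.01 = 1 point |
| 40% vs 25% | 20 points | 0.08 − 0.05 = 3 points |

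The sign reverses if the arms are swapped.

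**4. Completers against the imputed analysis.** This is the choice at issue. Let e be the share of the gap that the T0, T2 and T3 data explain. Then

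difference = e1·m1·g1 − e3·m3·g3.

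With e = 0.5 in both arms, the last two rows give 0.5 and 1.5 points. The second is 0.015 / 0.0354 = 0.42 of a standard error, where the standard error is for 360 versus 450 responders at 50%.

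**5. Single trials.** A simulation used 600 per arm, 1,500 trials and 20 imputations by arm and T0 status, with assumed inputs chosen so that e = 0.5. With 40% missing in both arms the two analyses agreed on average, but their difference had an SD of about 1.3 points. With an assumed true effect of 8 points and the plan's cut-off of 2.15 standard errors, they disagreed on significance in about 12% of trials. With 40% versus 25% missing they disagreed in about 16%.

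**6. Later time points.** Change from baseline is analysed at T2 and T3. Read literally, the rule removes a person who missed T1 but answered T2 or T3.

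**The case against.** A coherent reading exists. The sentence on all randomized participants stands under a heading about adherence and serves to separate ITT from as-treated; section 4.8.2 explains ITT as analysis by assigned arm. On that view one sentence fixes the grouping, the next fixes the data needed for the default z-test, and imputation is conditional. The naive analysis is presented as preliminary, follow-up surveys go to all arms on one schedule with the same $30 payment, response rates will be reported, and the DSMB statistician replicates the result.

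Much of this stands. The common schedule and payment make differential response less likely, though they do not exclude it, and reporting makes an undisclosed switch harder. But none of it ranks the two analyses, and the replicating statistician would face the same ambiguity. Confining imputation to secondary items or later surveys does not fit either, because the text names primary outcomes and gives T1 as its example.

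A reader might infer that the primary result is already biased, perhaps because section 4.4.2 reports low webinar attendance. Attendance is not T1 survey response, and the documents give neither response rates by arm nor a responder gap. A reader might also take the completer bias as a ceiling on what the choice can change. It is not: with m = 0.40 and g = 0.20 in both arms, e1 = 1 and e3 = 0.5, the completer bias is 0 but the analyses differ by 0.08 − 0.04 = 4 points.

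**Conclusion.** The concern holds as a conflict between stated rules with no ranking. The plan does not say whether the completer or the imputed analysis is primary, or which of them the 0.016 threshold applies to. It should be settled before any outcome analysis because it concerns the primary comparison. The T2 and T3 loss is a lesser consequence, since no threshold is set for those outcomes.

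The size cannot be fixed from the documents. Expected disagreement is zero if losses are random, as section 4.6 assumes for power. The 1-point and 3-point completer biases, and the simulated disagreement, rest wholly on assumed missingness, gaps and predictive strength. The documents support neither a claim that no coherent reading exists nor a claim of demonstrated bias.

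**What to change.** Amend Appendix B as follows.

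1. Remove the T0-and-T1 sentence as the inclusion rule and keep it only as the definition of a labelled completer sensitivity analysis.
2. Define the primary analysis set as all randomized participants in their assigned arm, except those unenrolled for failed verification (section 4.7.2) and those removed under the existing fraud rule: "Upon discovery of compelling evidence of fraudulent or illegitimate enrollment, such subjects will be excluded from the study prior to any outcome analyses". Reconcile the removal of contaminated data in section 4.1.5 with this set.
3. If T1 confidence is more than 5% missing in that set, make the planned multiple imputation the primary estimator to which the Multiple testing thresholds apply, with arm in the model and T0, T2 and T3 confidence as predictors.
4. At 5% or less missing, make the available-case analysis of observed T1 data by assigned arm the primary estimator, and label it as such.
5. Do not require T1 data for the T2 and T3 change-from-baseline analyses.

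Naming completers as primary and imputation as a sensitivity analysis would also end the ambiguity, but it would keep the selection on response after allocation.

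The cost is SAP wording and a little extra analysis work; the surveys and the imputation are already planned. Imputation removes only the part of any bias that the T0, T2 and T3 data explain.

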4.4.2 Development

The overall designs of the dialogue-based webinar and social media website interventions were informed by prior studies^{22,23,26} and developed using participatory research approaches^{40,41}. In developing content for each intervention, our goal was to maximize consistency of major topics across interventions, in order to isolate effects of each intervention delivery method.

To inform the intervention content, we initially derived topics from several sources, including social media monitoring, news surveillance, online public opinion polls^{42,43}, and peer-reviewed literature³⁹. The major topics for inclusion in both interventions were then refined via interviews with our LTCW partners as part of Aim 3. Additional information was gathered to inform the development of the social media website intervention, the details of which are published

elsewhere⁴⁴. The final list of major topics includes COVID-19 in general, vaccine benefits, vaccine risks, and vaccine development⁴⁴.

We also developed community standards to ensure all participants felt welcome and comfortable when engaging with the interventions. These standards, which are similar across both interventions, were based on the rules of existing vaccine discussion forums and were co-created with our LTCW partners⁴⁴. Also included in both interventions is a video that we developed featuring LTC residents voicing their views on why it is important for LTCWs to be vaccinated.

In response to low intervention exposure in one trial arm (webinar attendance) experienced in the first several weeks of data collection, we developed intervention ‘refreshers’ for each trial arm. The refreshers for trial arms 1 and 2 are briefer, modified versions of each primary intervention. They include content on new and emerging COVID-19 and vaccine-related topics, as well as popular questions trial participants have voiced through their primary intervention engagement. New and emerging topics were derived from several sources, including social media monitoring, news surveillance, online public opinion polls⁴⁵, and consultation with our LTCW partners and other stakeholders. Topics for inclusion were refined primarily via a poll to identify stakeholders’ information needs (process adapted from⁴⁶). Refreshers for trial arms 1 and 2 will be updated as required when there is sufficient new and emerging COVID-19 related public discourse.

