4.4.3 Intervention 1: Dialogue-Based Webinar

LTCWs will attend one-time virtual webinars in groups of no more than 20, scheduled at different times, and different days (including weekends). Each webinar will be led by a LTCW peer trained in SDM principles. It will also be co-facilitated by a physician with expertise in COVID-19 vaccination, and a communication expert with experience in SDM.

The webinar intervention agenda is as follows: i) the LTCW facilitator will introduce the session and go over important instructions, including the set of community standards, ii) the physician facilitator will review the COVID-19 vaccine Option Grid™ conversation aid (see Appendix A) and other related topics of interest using the principles of the SDM three-talk model⁴⁷. A link to the online Option Grid™ will also be sent to participants prior to their webinar commencing iii) participants will then be presented with the four major content topics pertaining to COVID-19 and the vaccines (consistent with those listed above in section 4.4.2) and will vote (via a poll) on the two content topics that matter most to them. The physician facilitator will then start by answering questions from participants related to the top voted content areas, and then open questioning up to all topics until there are no remaining queries. The webinars will end with the LTC resident video described earlier.

Throughout the webinars, the communication expert will assist with any related discussions where needed and respond to study-related questions/issues or technical troubleshooting. Webinar durations will vary, running up to 1 hour, or less if there are no remaining questions. Participants will also be invited to join a facilitated online discussion in the webinar chat and their engagement will be monitored (e.g., number of chat messages posted during each webinar and webinar content).

A dialogue-based webinar refresher will also be delivered to all participants in this arm one week prior to their T2 survey invitation (see Figure 2). The refresher will be a pre-recorded webinar (video and audio-only versions) lasting ~20 minutes, sent to participants via email. The structure of the recorded webinar will closely resemble that of the primary intervention, and will include a review of the COVID-19 Option Grid™, question and answer discussion, and LTC resident video. It will be available to participants as a video and an audio-only recording.

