4.7.5 Follow-up Assessments

Participants will be invited to complete three follow-up surveys. For all participants, the follow-up surveys will be delivered three weeks post-baseline survey/randomization (T1), three months post-baseline survey (T2), and six months post-baseline survey (T3).

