- *Feeling informed about the COVID-19 vaccines*. The degree to which participants' feel informed about the COVID-19 vaccines (have enough information and understand that information) will be evaluated using a continuous variable, calculated as the mean scale

score across two items ((1) having enough information, (2) understanding the information) for each participant. The mean of all mean scores will be compared across trial arms with two-sample unpaired t-tests.

- *Identification of COVID-19 vaccine information and misinformation.* Subjects' identification of COVID-19 vaccine information and misinformation will be scored on a scale of zero to four and treated as a continuous linear variable. Results will be compared across trial arms with two sample unpaired t-tests.
- *Trust in COVID-19 information from different sources.* Subjects' trust in COVID-19 information from different sources will be evaluated using a continuous variable, calculated as the mean scale score across three items for each participant. The mean of all mean scores will be compared across trial arms with two-sample unpaired t-tests.
- *Change from baseline in secondary outcomes.* Change from baseline will be scored as a binary variable with an increased value scored as one and a no change or decreased value scored as zero. For each evaluation after baseline, each arm will be compared using two-proportion z-tests. For vaccine and booster intent questions, where the intent question is not repeated if the participant indicates an increase in vaccination status, intent will be imputed from uptake. To be clear, an individual who is unvaccinated at T0, then returns at T1 and indicates that he or she is now vaccinated, will be presented with the vaccine intent question at T0 but not at T1. Because the individual is now vaccinated, asking about vaccine intent at T1 would be confusing. For analyzing change in vaccine intent, the individual whose vaccine status increases would be considered to have positive intent at T1. A similar approach will be used for booster intent.
- *As treated analysis of primary and secondary outcomes.* Primary and secondary outcome analyses will be repeated, limited to the as treated samples.

Aim 2

To determine if LTCWs' characteristics and other factors mediate and moderate the interventions' impact on vaccine confidence and other secondary outcomes.

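### Read literally, the T0-and-T1 entry rule keeps workers who skip T1 out of the T2/T3 change comparisons, and the plan does not reconcile it with its ITT and imputation text

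*Combined protocol and SAP*

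**What the plan says.** All of the following is in Appendix B unless another section is named.

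- **Entry rule** (Duplicate and missing data): "In order to be included in primary and secondary outcome analyses, participants must have valid primary outcome data at both T0 and T1". No exception is written for any wave or outcome.
- **Primary outcome**: confidence is "evaluated at 3 weeks post-randomization, which will be analyzed by randomization arm", so it is a T1 outcome.
- **Later waves**: change in confidence is coded by whether the average score "increases (1) or does not increase (2) at T1, T2, and T3 versus baseline". For change in the other secondary outcomes: "For each evaluation after baseline, each arm will be compared using two-proportion z-tests". In Appendix B Table 1 the two change-from-baseline rows and the as-treated row are ticked from T0 to T3. The other outcome rows are ticked at T1 only.
- **Who is surveyed** (section 4.7.5): all three follow-up surveys go to every participant, so answering T1 is not a condition for being sent T2 or T3.
- **ITT population** (Adherence to interventions): everyone randomized is included.
- **Missing data**: if an outcome is more than 5% missing, the reasons are examined, including for "those who did not respond to one or more evaluations but were not lost to follow-up". Multiple imputation, as appropriate, then supports an analysis of the whole data set. The plan's own example uses T0 and T2 to fill in T1.
- **Methods to minimize bias**: an initial analysis uses unmodified data by assigned arm.

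**The concern.** A change from T0 to T2 can be computed without T1. A rule that demands T1 anyway sets aside data already in hand and selects participants on something that happens after randomization.

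That selection is plausibly related to arm. The trial is open-label (section 4.7.4), and T1 response is likely to track engagement. Section 4.4.2 explains why refreshers were added: "In response to low intervention exposure in one trial arm (webinar attendance) experienced in the first several weeks of data collection". Section 4.4.3 says: "A dialogue-based webinar refresher will also be delivered to all participants in this arm one week prior to their T2 survey invitation". The other two arms also receive a refresher at that time. A worker who drifted away early, is reached again and then answers T2 is the kind of participant the entry rule leaves out.

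If webinar attenders answer T1 more often than non-attenders, the filtered webinar arm holds too many attenders, with no matching shift in the control arm. The T2 and T3 comparisons are the trial's between-arm evidence on whether any effect persists.

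**Working it through.** **1. The texts side by side.** Take a worker with T0 and T2 answers and no T1 answer.

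| Text in Appendix B | In the T2 change comparison? |
|---|---|
| Entry rule | No |
| ITT definition | Yes |
| Imputation text | Yes, if an imputed T1 counts as valid; not stated |
| Initial analysis on unmodified data | Nothing is imputed, so no, if the entry rule applies to it |

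The order of steps matters. If the entry rule is applied first, no T1 confidence score is missing in the resulting set, so for that score the plan's own imputation example cannot arise.

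**2. The plan's power figure.** Section 4.6 gives 600 per arm, an 8-point difference, two-sided 0.05 and 80% power; and 10 points after 40% attrition, which leaves 600 × 0.60 = 360 per arm. No control rate is given. For a pooled two-proportion z-test, power = Φ{[√n·Δ − 1.96·√(2p̄(1−p̄))] / √(p₁(1−p₁)+p₂(1−p₂))}.

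- n = 600, 40% vs 48%: (1.960 − 1.376)/0.700 = 0.834, power 0.798.
- n = 360, 30% vs 40%: (1.897 − 1.322)/0.671 = 0.858, power 0.804. At 45% vs 55% it is 0.766.

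The stated figures reproduce at plausible control rates.

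**3. Precision.** Assume 360 per arm answer T2 and a share q of them skipped T1. The rule leaves 360(1−q). Power is for 30% vs 40% and serves only as a yardstick.

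| q | analysed per arm | power |
|---|---|---|
| 0 | 360 | 0.804 |
| 5% | 342 | 0.784 |
| 10% | 324 | 0.762 |
| 20% | 288 | 0.712 |
| 30% | 252 | 0.654 |

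**4. Selection with no true difference.** Assume 45% are confident in both arms and 30% among T1 skippers. With 10% skipping in one arm and 20% in the other, the filtered rates are (0.45 − 0.10×0.30)/0.90 = 46.7% and (0.45 − 0.20×0.30)/0.80 = 48.8%, a spurious gap of about 2 points. With equal skipping the gap is zero.

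**5. Webinar against control, two strata (would attend, would not).** Assumptions: 600 per arm; attendance 40% or 60%; T1 response 90% in attenders, 60% in non-attenders, 75% in control; T2 response 85% after answering T1, and 30% or 50% after skipping it; true T2 difference 8 points; non-attenders gain 0 or 3 points; control rate 40% in would-be attenders and 40% or 32% in the rest. This gives 16 scenarios.

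*Largest effect of the filter* (attendance 40%, return 50%, non-attenders gain 0, other-stratum rate 32%). Attenders gain 8/0.4 = 20 points, to 60%.
- Answer T1 and T2: attenders 240×0.9×0.85 = 183.6; non-attenders 360×0.6×0.85 = 183.6. Rate (183.6×0.60 + 183.6×0.32)/367.2 = 46.0%.
- Answer T2 only: 240×0.1×0.5 = 12 and 360×0.4×0.5 = 72. Rate among all T2 respondents (195.6×0.60 + 255.6×0.32)/451.2 = 44.1%.
- Control: 0.4×40% + 0.6×32% = 35.2% either way.
- Differences 10.80 and 8.94 points, so the filter adds 1.86. Dropped: 84/451.2 = 18.6%. Standard-error factor 1/√(1−0.186) = 1.11.

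*Smallest effect* (attendance 60%, return 30%, non-attenders gain 3, rate 40% throughout). Attenders gain (8 − 0.4×3)/0.6 = 11.33 points.
- Filtered: (275.4×0.5133 + 122.4×0.43)/397.8 = 48.77%, difference 8.77.
- All T2 respondents: (286.2×0.5133 + 151.2×0.43)/437.4 = 48.45%, difference 8.45.
- The filter adds 0.32. Dropped: 39.6/437.4 = 9.1%. Standard-error factor 1.05.

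Over all 16 scenarios the filtered difference is 8.77 to 10.80 and that for all T2 respondents 8.27 to 9.59, against a true 8.00. With only 10% of T1 skippers returning, the filter adds 0.1 to 0.4 points, drops 3% to 4%, and widens standard errors by about 2%.

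**The case against.** The strongest reply is that the plan does not clearly drop these workers. The ITT definition includes everyone randomized, and the imputation example is precisely a person with T0 and T2 but no T1. With 40% attrition allowed for, the 5% trigger would very probably be met. This stands: a reader might infer that T1 skippers are definitely excluded and that T2/T3 results describe T1 responders only, but the documents support that only as the literal reading of one sentence that others contradict. The reply does not settle the matter, because nothing says that an imputed T1 is valid. Even on the generous reading, an observed T2 answer would be admitted only after imputing a T1 score that the comparison does not use.

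Other limits also stand:

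- A reader might take the whole excess over 8 points in step 5 (10% to 35%) as the cost of the rule. Part of it is ordinary T2 non-response, which dropping the rule does not cure: 0.3 to 1.6 points remain. At 30% return the filter accounts for less than half of the excess in every scenario.
- The illustration models the level of binary confidence, whereas the planned T2/T3 confidence outcome is whether the average score rose. The assumed T1 response pattern also fixes the direction of the bias.
- A reader might infer that one blank confidence item at T1 removes all of a worker's other T1 outcomes. The plan does not define valid, and the scoring in section 4.5.1 could allow a partly completed index to be classified.
- T2/T3 cannot isolate the refreshers, because all arms receive one. Engagement and process-evaluation data also bear on them.
- Secondary outcomes have no significance threshold (Multiple testing), which lowers the stakes.

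**Conclusion.** The point holds as an unresolved contradiction with a specific consequence on one reading. If the entry rule governs, collected T2/T3 answers go unused and the later-wave comparisons are conditioned on T1 response. If the ITT and imputation text governs, this need not happen. Two analysts could follow the plan faithfully and report different T2/T3 populations.

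The size cannot be determined from the documents. Under the step 5 assumptions the filter's own contribution is 0.3 to 1.9 points, at most about half of a standard error of about 3.6 points, with 9% to 19% of T2 respondents dropped and standard errors 5% to 11% wider. It shrinks as fewer T1 skippers return. If T1 response is unrelated to arm and engagement, only precision is lost.

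At T2/T3 the affected results are the change-from-baseline outcomes and their as-treated versions. The point should be settled before analysis, but it does not bear on the T1 primary comparison.

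**What to change.** Limit the T0-and-T1 condition so that it no longer governs secondary outcomes. Do not simply delete it: the same sentence also defines the primary analysis set, which needs its own explicit sentence. Then add:

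> For each secondary outcome at T1, T2 or T3, all randomized participants with an observed value at that wave (or, for intent, a value derived from uptake as described above), and at T0 where change is analysed, are included in their assigned arm, whether or not they have a valid confidence score at T1. Missing values are handled by the stated multiple imputation.

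Align this with the ITT definition, and state whether an imputed T1 satisfies any entry condition that remains. Report how many respondents at T2 and T3 had skipped T1. The T1-responder set can be kept as a sensitivity analysis if wanted.

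The cost is a few sentences of SAP text and no new data. Denominators will differ by outcome and wave, so each table must show its own.
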